**Table 1 Dose-Limiting Toxicities (DLT)**

Toxicity Category	Toxicity/CTCAE Grade
Hematological Toxicity	
 
• Grade 4 neutropenia for > 7 days or neutropenia requiring hematopoietic growth factors
 
• ≥ Grade 3 febrile neutropenia
 
• Grade 4 thrombocytopenia, Grade 3 thrombocytopenia with bleeding, or thrombocytopenia requiring platelet transfusion
 
• Grade 4 anemia or anemia requiring erythrocyte transfusion
 

Non-hematological Toxicity	
 
• ≥ Grade 3 nausea, vomiting, or diarrhea that persists > 7 days despite maximal medical therapy
 
• ≥ Grade 3 non-hematological laboratory abnormalities with clinical symptoms that persists > 7 days
 
• Other Grade 3 toxicity lasting > 7 days or Grade 4 non-hematological toxicity of any duration
 

Medication compliance	
 
• Failure to administer ≥ 75% (≥ 42/56 doses) of the planned administration number of study drug in Cycle 1 as a result of treatment-related toxicity
 

## 9.2 Discussion of Study Design, Including Choice of Control Groups

This study was designed according to “The Guidelines for Clinical Evaluation of Anti-Cancer Drugs in Japan (Notification No. 1101001 issued on 01 Nov, 2005).”

### 9.3 Selection of Study Population

Approximately 6 subjects will be enrolled at approximately 2 sites in Japan. Subjects who do not meet all of the inclusion criteria or who meet any of the exclusion criteria will not be eligible to receive study drug.

#### 9.3.1 Inclusion Criteria

Subjects must meet all of the following criteria to be included in this study:

- (1) Patients with histological diagnosis of B-cell NHL (except transformed lymphoma) as follows:
  - Diffuse large B-cell lymphoma (DLBCL)
  - Follicular lymphoma (FL)
- (2) Patient who has measurable disease as below.
  - Lymph node or ex-nodal disease diagnosed by CT scan.
  - Clearly measurable in 2 orthogonal ways by CT scan.
  - $\geq 1.5$  cm in long axis or  $> 1.0$  cm in short axis, when long axis were  $< 1.5$  cm.
- (3) Patient who had previous therapy with systemic chemotherapy and/or antibody therapy and for which no standard therapy exists.
- (4) Patient who was PD or did not have response (complete response [CR] or partial response [PR]) in previous systemic therapy, or relapsed or progressed after previous systemic therapy.
- (5) Patient with Eastern Cooperative Oncology Group (ECOG) performance status of 0 to 1
- (6) Patient with life expectancy of  $\geq 3$  months from starting study drug administration.
- (7) Patient with adequate renal function:
  - Serum creatinine  $\leq 1.5 \times$  upper limit of normal (ULN)
- (8) Patient with adequate liver function:
  - Total bilirubin  $\leq 1.5 \times$  ULN
  - Aspartate aminotransferase (AST) and alanine aminotransferase (ALT)  $\leq 3.0 \times$  ULN
- (9) Patient with adequate bone marrow function:
  - (confirm 2 weeks or later from last administration of granulocyte colony-stimulating factor [G-CSF] and blood transfusion, if these are used)
  - Absolute neutrophil count  $\geq 1.5 \times 10^3 / \mu\text{L}$  ( $\geq 1.5 \times 10^9 / \text{L}$ )
  - Platelet count  $\geq 10.0 \times 10^4 / \mu\text{L}$
  - Hemoglobin  $\geq 9.0$  g/dL
- (10) Patient with left ventricular ejection fraction (LVEF)  $> 50\%$  on echocardiography or multiple gate acquisition (MUGA) scan.
- (11) Patient with time between prior anti-tumor therapy and first administration of study drug as below:
  - Cytotoxic chemotherapy – At least 3 weeks
  - Non-cytotoxic chemotherapy (eg, corticosteroids\*, small molecule inhibitor) – At least 2 weeks
  - Monoclonal antibody (ies) – At least 4 weeks

- Radiotherapy
    - At least 3 weeks from radiation therapy
    - At least 6 weeks from prior radioisotope therapy
  - Autologous hematopoietic stem cell transplantation – At least 6 months
    - \*: Patient may receive no more than 10 mg of prednisolone daily or equivalent corticosteroid when used for treatment of lymphoma-related symptoms.
- (12) Patient with no carry-over of  $\geq$  Grade 2 adverse events of the prior treatment that may affect the safety evaluation of the investigational drug.
- (13) Male and female patient  $\geq$ 20 years of age at the time of informed consent.
- (14) Patient who has provided written consent to participate in the study

### 9.3.2 Exclusion Criteria

Subjects who meet any of the following criteria will be excluded from this study:

- (1) Patient with prior exposure to EZH2 inhibitor.
- (2) Patient with a history or a presence of central nerves invasion.
- (3) Patient with malignant pleural effusion, cardiac effusion, or ascites retention.
- (4) Patient with allogeneic stem cell transplantation.
- (5) Patient with medical need for the continued use of potent or moderate inhibitors of CYP3A or P-gp, or potent or moderate inducer of CYP3A (including St. John's wort). Patient is eligible if 2 weeks or longer have passed since the last use of such agents prior to the first dose of study drug.
- (6) Patient unwilling to exclude grapefruit (juice) from the diet for 1 week prior to study drug administration and throughout the study.
- (7) Patient with achlorhydria or use of H2 blockers or proton-pump inhibitors within 2 weeks before study drug administration.
- (8) Patient with inability to take oral medication, or malabsorption syndrome or any other uncontrolled gastrointestinal condition (eg, nausea, diarrhea, or vomiting) that might impair the bioavailability of study drug.
- (9) Patient with significant cardiovascular impairment
  - History of congestive heart failure  $\geq$  New York Heart Association (NYHA) Class III
  - Uncontrolled arterial hypertension, unstable angina, myocardial infarction, or stroke within 6 months of the first dose of study drug
  - Ischaemic heart disease, cardiac arrhythmia requiring medical treatment
- (10) Patient with prolongation of corrected QT interval using Fridericia's formula (QTcF) to  $>$  480 msec.
- (11) Patient with venous thrombosis or pulmonary embolism within the last 3 months before starting study drug.
- (12) Patient with complications of hepatic cirrhosis, interstitial pneumonia or pulmonary fibrosis.
- (13) Patient with active infection requiring systemic therapy.
- (14) Patient with known hypersensitivity to any component of study drug.
- (15) Patient who is positive for HIV antibody, HCV antibody, or HBs antigen. Patient who is positive for HBs or HBc antibody and showing DNA more than sensitivity in HBV-DNA assay.

- (16) Patient with malignancy of activity other than B-cell NHL within 36 months before informed consent (except treated non-invasive melanoma, basal cell carcinoma of the skin or squamous cell carcinoma, intraepithelial carcinoma such as uterine cervix).
- (17) Women of childbearing potential or man of impregnate potential who don't agree that both the patient and his/her partner will use a medically effective method for contraception (as below) for periods from before informed consent to during the clinical study and 30 days later (for males 90 days later) from last administration of study drug.
- (18) Woman with pregnant or breastfeeding (not eligible even if she discontinues breastfeeding).
- (19) Patient who was decided as inappropriate to participate in the study by the investigator or subinvestigator.

Note: Condom\*, contraceptive sponge\*\*, foam\*\*, jelly\*\*, diaphragm\*, intrauterine device (IUD)\*, or use of oral contraception\* at least 30 days before starting the study treatment

(\*Approved drugs or certified medical devices in Japan, \*\*Non-approved drugs or certified medical devices in Japan)

### 9.3.3 Removal of Subjects From Therapy or Assessment

The investigator or subinvestigator may discontinue treating a subject with study treatment or withdraw the subject from the study at any time for safety or administrative reasons. The subject may decide to discontinue study treatment or withdraw from the study at any time for any reason. The reason for discontinuation will be documented. If a subject discontinues study treatment, the subject will enter the Follow-up Phase and complete protocol-specified off-treatment visits and procedures unless the subject withdraws consent. If a subject withdraws consent, the date will be documented in the source documents. The CRF will be completed indicating the primary reason for discontinuation. In addition, the date of last dose of study drug will be documented on the CRF.

#### 9.3.3.1 Discontinuation Criteria by Subject

If a subject meet any of the following criteria, the investigator or subinvestigator will discontinue treating the subject with study treatment. If a subject experiences myeloid malignancy including myelodysplastic syndrome, study treatment should be interrupted and restart (including dose modification)/discontinuation of study treatment should be discussed with the sponsor. If a subject experiences T-cell lymphoblastic lymphoma/T-cell acute lymphoblastic leukemia, study treatment should be discontinued and other actions should be discussed with the sponsor.

- (1) Withdrawal of consent or proposal to refuse continuation of participation by the subject
- (2) Major violation of inclusion or exclusion criteria are found.
- (3) Presence of adverse event that is judged by the investigator or subinvestigator to prohibit continuation with therapy
- (4) Pregnancy
- (5) Evidence of disease progression. Subjects will be allowed to be treated with study drug

if the investigator judges that the administration of the study drug is clinically beneficial for the subject.

- (6) Subject is turned to be non-compliant with the protocol and ineligible in view of safety issue.
- (7) Study discontinuation is appropriate judged by the investigator or subinvestigator.
- (8) Subject experiences T-cell lymphoblastic lymphoma/T-cell acute lymphoblastic leukemia.

## 9.4 Treatment

### 9.4.1 Treatment Administered

Tazemetostat 800 mg will be administered orally by single dose in Cycle 0/Day 1 (C0D1) and continuous BID (1600 mg total daily dose, no less than 8 hours between doses except C1D15 that requires 12 hours or more) in Cycle 1 and later, in a fasted state on C0D1 and at the first administration of C1D15 defined as either  $\geq 2$  hours before and  $\geq 2$  hours after a meal (only water is allowed).

#### 9.4.1.1 Tazemetostat Dose Reduction and Interruption Instructions

##### 9.4.1.1.1 CYCLES 0 AND 1

#### **If DLT occurs:**

Tazemetostat administration should be interrupted immediately. Treatment may be resumed in Cycle 2 at 600 mg BID (1200 mg total daily dose) if toxicity is resolved to Grade  $\leq 1$  or baseline and the investigator or subinvestigator decides to continue the study.

#### **No DLT:**

Tazemetostat administration will be interrupted if judged to be clinically needed by investigator or subinvestigator, and may be resumed at the same dose level at appropriate timing.

##### 9.4.1.1.2 CYCLE 2 AND LATER

Dose reduction and interruption for subjects who experience tazemetostat-related toxicity will follow the instructions shown in [Table 2](#). Dose reductions will be based on the previous dose level in order of 600, 400 mg BID (1200 mg, 800 mg total daily dose, respectively). Once the dose is reduced, it cannot be increased at a later date. Any dose adjustment must be discussed with the sponsor or discontinue tazemetostat when toxicities requiring dose reduction occur at the dose of 400 mg BID.

If a subject experiences myeloid malignancy including myelodysplastic syndrome, study treatment should be interrupted and restart (including dose modification)/discontinuation of study treatment should be discussed with the sponsor. If a subject experiences T-cell

lymphoblastic lymphoma/T-cell acute lymphoblastic leukemia, study treatment should be discontinued and other actions should be discussed with the sponsor.

Study treatment may be interrupted, also if it is required to ensure the safety of a subject experiencing an adverse event that is unrelated to the study drug. In such cases, study treatment should be resumed as soon as possible, at the same dose as had been administered before the interruption.

**Table 2 Tazemetostat Dose Reduction and Interruption Instructions**

Tazemetostat -related Toxicity		During Therapy d	Dose adjustment d
Grade 1 and Tolerable Grade 2 a		Continue tazemetostat	Maintain dose level
Intolerable Grade 2 a and Grade 3 b		Interrupt tazemetostat until resolved to Grade $\leq$ 1 or baseline c	Dose reduction by one dose level
Grade 3 and Grade 4 neutropenia	ANC $\geq 0.75 \times 10^9/L$	Continue tazemetostat	Maintain dose level
	ANC $< 0.75 \times 10^9/L$	Interrupt tazemetostat until resolved to ANC $\geq 0.75 \times 10^9/L$ e	Dose reduction by one dose level
Grade 4 c		Interrupt tazemetostat until resolved to Grade $\leq$ 1 or baseline c	Discuss with sponsor or discontinue tazemetostat

ANC = absolute neutrophil count.

a: Tolerability of Grade 2 toxicities will be judged by the study investigators.

b: Dose interruption and reduction is not necessary for Grade 3 thrombocytopenia, anemia and Grade 3 or 4 leukopenia, lymphopenia and laboratory abnormalities that are not clinically relevant. Initiate optimal medical management for nausea, vomiting, and/or diarrhea prior to any study treatment interruption or dose reduction.

c: Laboratory abnormalities judged to be non-life threatening, will be managed as Grade 3.

d: Discuss with the sponsor when to consider the dose interruption and adjustment other than instructions.

e: To minimize the duration of interruption, assessment at least every 7 days is recommended. A delay of tazemetostat for more than 28 days due to any toxicity must be discussed with the sponsor before treatment can be resumed.

#### 9.4.2 Identity of Investigational Product

[figure not shown]
Tazemetostat will be provided as 200 mg tablet by the sponsor. Tazemetostat tablets contain 200 mg of drug substance as the free base.

##### 9.4.2.1 Chemical Name, Structural Formula of Tazemetostat

- Test drug code: E7438
- Generic name: tazemetostat (INN)
- Chemical name: *N*-[(4,6-Dimethyl-2-oxo-1,2-dihydropyridine-3-yl)methyl]-5-[ethyl(tetrahydro-2*H*-pyran-4-yl)amino]-4-methyl-4'-(morpholin-4-ylmethyl)biphenyl-3-carboxamide hydrobromide
- Molecular formula: C34H44N4O4Br

- Molecular weight: 653.65
- Structural formula:

#### 9.4.2.2 Comparator Drug

Not applicable.

#### 9.4.2.3 Labeling for Study Drug

The following information is provided on the study drug labeling. Details on labeling and package are shown in the Attachment separately provided to each site.

- For clinical study use only
- Name and address of the sponsor
- Drug identifier
- Lot number/batch number
- Storage conditions

#### 9.4.2.4 Storage Conditions

Study drug will be stored in accordance with the labeled storage conditions. The assigned pharmacist or designee is responsible for ensuring that the temperature is monitored throughout the total duration of the study, that the study drug is maintained within an established temperature range, and that records are maintained; the temperature should be monitored continuously by using either an in-house data acquisition system, a mechanical recording device, such as a calibrated chart recorder, or by manual means, such that minimum and maximum thermometric values over a specific time period can be recorded and retrieved as required.

#### 9.4.3 Method of Assigning Subjects to Treatment Groups

This is an open-label, single-arm study. All subjects who provide signed informed consent and satisfy all eligibility requirements (see [Section 9.3](#)) will receive study drug. There is no randomization in this study.

- (1) The investigator, subinvestigator, or clinical research coordinator will issue the Subject ID Number to individual subjects who provide signed informed consent for study entry and record it in "Subject Screening Log."
- (2) The investigator, subinvestigator, or clinical research coordinator will screen the subjects

and determine subject eligibility based on the inclusion and exclusion criteria. The investigator, subinvestigator, or clinical research coordinator will record the decision on the subject eligibility in the “Subject Screening Log.”

- (3) The investigator, subinvestigator, or clinical research coordinator will notify the sponsor of date of informed consent, date of screening initiation, and eligibility decision by email or fax immediately after the investigator or subinvestigator determines the subject eligibility.
- (4) After the sponsor confirms the subject eligibility, the investigator or subinvestigator will be informed of the date of registration and dose to be administered by email or fax (subject registration).
- (5) The investigator or subinvestigator will confirm the subject registration and then confirm the subject eligibility based on the results of screening according to the inclusion and exclusion criteria. The investigator or subinvestigator will record the subject eligibility in medical charts and initiate study drug administration.

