##### 9.1.1.1 Pre-treatment Phase

The Pre-treatment Phase will last no longer than 28 days and include a period to obtain informed consent, screening, enrollment, and a baseline assessment. Informed consent will be obtained after the study has been fully explained to each subject and before the conduct of any screening procedures or assessments. After screening assessments, the patient who meets the inclusion criteria and does not meet the exclusion criteria will be enrolled. The baseline assessment will be conducted within 3 days before the treatment in order to confirm

that the patient continues to meet the inclusion criteria and does not meet the exclusion criteria before moving to the Treatment Phase.

The CRF must be completed to indicate whether the subject is eligible to participate in the study and to provide reasons for screen failure, if applicable.

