**Table 6 Schedule of Procedures/Assessments in Study E7438-J081-106 (EZH-106)**

Phase	Pre-treatment		Treatment						Extension		Follow-up	
Period	Screening a	Baseline	Cycle 0	Cycle 1					Cycle 2 and later		Discontinuation	Final observation
Day	Within 28 days before administration	Within 3 days before administration	1	1 b	3	8 (±1)	15 (±1)	22 (±1)	1 (±3) c	15 (±3) n	(+7)	30 days after last dosing (+7) d
Informed Consent	X								[X] m			
Demographic data	X											
Inclusion/exclusion Criteria	X	X										
Medical history/Current medical condition	X											
Previous therapy	X											
Height	X											
Body weight	X	X		X		X	X	X	X	X	X	
Physical examination	X	X	X	X		X	X	X	X	X	X	X
Vital signs	X		X	X		X	X	X	X	X	X	X
ECOG-PS	X	X		X					X		X	
12-lead ECGs e	X		X	X			X		X	X	X	
Echocardiogram or MUGA scan f	X								[X]			
Pregnancy test (if applicable)	X										X	
Virus test	X											
Hematology o	X	X		X		X	X	X	X	X	X	X
Blood chemistry	X	X		X		X	X	X	X	X	X	X
Urinalysis	X	X		X		X	X	X	X	X	X	X
PK (blood) g			X		X	X	X	X	[X]			
PK (urine) h			X				X					
Tumor assessments (CT) i	X									[X]	X	
Bone marrow aspiration or biopsy j	X									[X]		
Tazemetostat administration k			X	Continuous 28-day cycle of tazemetostat twice daily.								
Archival tumor sample submission l				X								
Adverse events				From informed consent to final observation								

Concomitant drug/therapies	From informed consent to final observation
----------------------------	--

Note, [X]: In case to perform.

C#/D# = Cycle #/Day #, CR = complete response, CT = computed tomography, ECG = electrocardiogram, ECOG-PS = Eastern Cooperative Oncology Group-Performance Status, MUGA = multigated acquisition, PK = pharmacokinetics.

a: Screening assessments may be used as baseline assessments if performed within 3 days of the first administration of study drug.

b: To start C1D1 on Cycle 0 Days 4-9.

c: +1 day for C2D1.

d: When subject needs to receive other anti-tumor therapy due to deterioration of the disease within 30 days after the final study drug administration, final observation must be conducted before initiation of other anti-tumor therapy and the data within 7 days before next anti-tumor therapy can be used for final observation. .

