e: 12-Lead ECGs on C0D1, C1D1, and C2D1 will be collected at pre-dose and 0.5-2 hours post dose of first administration.

f: Echocardiogram or MUGA scan will be performed at screening, every 16 weeks (ie, Day 1 of every 4 cycles [ $\pm$  1 week]) from C2D1. Additional assessments may be performed if clinically indicated.

g: Blood samples for PK analyses of tazemetostat and metabolites will be collected in C0D1 at predose, 0.5, 1, 2, 4, 6, 8, 10, 12, 24, 48 and 72 hours postdose; C1D3 and C1D8 at predose of first administration; C1D15 at predose of first administration, 0.5, 1, 2, 4, 6, 8, 10, and 12 hours postdose (postdose blood samples should be collected before the second administration of study drug); C1D22 and C2D1 predose of first administration.

h: Urine samples for PK analyses of tazemetostat will be collected in C0D1 at predose, 0-24, 24-48 and 48-72 hours postdose; C1D15 at 0-12 hours postdose of first administration.

i: The data of tumor assessments before informed consent within 28 days from study drug administration can be used as screening data if it meets the requirement of the protocol. Perform tumor assessment at screening, every 8 weeks [ $\pm$ 1 week] (starting at Cycle 1 Day 1) during Cycles 2-6, every 12 weeks [ $\pm$  1 week] starting at Cycle 7 and beyond, and discontinuation. The data within 28 days can be used as discontinuation data.

j: The data of bone marrow aspiration or biopsy before informed consent within 42 days from study drug administration can be used as screening data if it meets the requirement of the protocol. After the study drug dosing, perform bone marrow aspiration or biopsy if the result of screening was positive or unconfirmed and when to confirm CR as best of response or if clinically indicated.

k: Subjects should not take study drug before evaluations are performed (except tumor assessments and peripheral blood smear morphology assessment), unless specified.

l: Submit pre-study drug treated tumor sample to central laboratory before final observation, as far as possible.

m: Informed consent should be obtained before initiating the study or before entering the Extension Phase when Cycle 2 or later administrations will be continued.

n: In Cycle 13 or later, visits and assessments on Day 15 can be omitted at the discretion of the investigator or subinvestigator, if there was no concern for safety of the subject.

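### The Baseline visit is meant to re-confirm eligibility within 3 days of dosing, but Table 6 schedules no pregnancy test after Screening, which may be 28 days before the first dose.

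*Protocol*

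**What the plan says.** Section 9.1.1.1 of the protocol sets out the order of events before treatment: consent, screening, enrollment of those who qualify, then a further check. "The baseline assessment will be conducted within 3 days before the treatment in order to confirm" that the patient still satisfies the inclusion criteria and still meets no exclusion criterion. The synopsis and SAP 3.2 say the same.

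Table 6 gives the two visits separate columns, Screening ("Within 28 days before administration") and Baseline ("Within 3 days before administration"). The row "Inclusion/exclusion Criteria" is marked in both. The row "Pregnancy test (if applicable") is marked at Screening and at Discontinuation and nowhere else. Section 9.5.1.5.7.3 requires an hCG test on serum or urine for women of childbearing potential and leaves the timing to Table 6.

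Exclusion 18 in 9.3.2 reads: "Woman with pregnant or breastfeeding (not eligible even if she discontinues breastfeeding").

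Section 9.4.3 step 5 describes the last action before dosing. After registration is confirmed, the investigator is to "then confirm the subject eligibility based on the results of screening according to the inclusion and exclusion criteria", then record eligibility and start study drug. Baseline results are not mentioned.

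**The concern.** The protocol promises a re-check of every criterion shortly before dosing, but schedules no test that could supply it for pregnancy. A woman who tests negative early in the screening window and conceives afterwards, or who was tested too early to be positive, can pass every scheduled check and be dosed.

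The next scheduled test is at discontinuation, and treatment is open-ended: Table 6 footnote n provides for Cycle 13 and later. The protocol treats pregnancy as serious. It is a reason to stop treatment under 9.3.3.1(4), and 9.5.4.2 requires withdrawal from the study.

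The wording of 9.4.3 step 5 adds to the problem, because a site that follows it literally looks only at screening results when it makes the final decision. What is at stake is first of all subject protection. Any effect on the DLT evaluation is secondary.

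**Working it through.** There is no sample-size, power or event figure to reproduce. The check is a reading of Table 6 and its footnotes against 9.1.1.1 and 9.4.3.

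| Table 6 row | Screening (up to 28 days) | Baseline (up to 3 days) | C0D1, before dose | Next scheduled |
|---|---|---|---|---|
| Inclusion/exclusion check | X | X | – | – |
| Pregnancy test | X | – | – | Discontinuation |
| 12-lead ECG | X | – | X (footnote e) | C1D1 |
| Hematology, chemistry, urinalysis | X | X | – | C1D1 |

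1. **Age of the pregnancy result at first dose.** The only required test before dosing is at Screening, so the result may be up to 28 days old. The stated re-confirmation window is 3 days. The possible excess is 28 − 3 = 25 days.

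2. **When the gap closes.** Footnote a lets screening assessments stand in for Baseline if done within 3 days of the first dose. In that case the test is recent enough and there is no gap.

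3. **Whether other text supplies a test.** Section 9.5.1.5.7.3 defers to Table 6 and adds none.

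4. **Whether screening in step 5 could include Baseline.** Section 9.1.1.1 lists screening, enrollment and baseline as separate elements, Table 6 gives them separate columns, and footnote a is needed before one can serve as the other. The word in step 5 therefore does not naturally cover Baseline.

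5. **The rest of exclusion 18.** Breastfeeding needs no laboratory test and can be covered by the Baseline criteria check. Only the pregnancy part depends on a missing test.

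6. **What is already collected.** Blood and urine are both taken at Baseline, and 9.5.1.5.7.3 accepts either.

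**The case against.** Three arguments on the other side deserve weight.

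**The Baseline check still applies.** Section 9.4.3 describes registration mechanics. Step 5 is silent on Baseline but does not override 9.1.1.1, and 9.4.3 opens by requiring that all eligibility requirements be satisfied. This stands. The step 5 point is an alignment of wording, not evidence that eligibility rests on screening results alone.

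**Contraception.** Exclusion 17 requires women of childbearing potential and their partners to use effective contraception from before consent, so conception between Screening and dosing needs contraceptive failure or non-adherence. This also stands and lowers the risk. It does not remove the gap, because the protocol already requires a test in addition to contraception. Equally, a test at Baseline would reduce, but not eliminate, the chance of missing a very early pregnancy.

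**The ECG.** A reader might infer from the empty ECG cell at Baseline that exclusion 10 (QTcF above 480 msec) also cannot be re-checked. The documents do not support that. Footnote e states "12-Lead ECGs on C0D1, C1D1, and C2D1 will be collected at pre-dose", footnote k places evaluations before study drug, and 9.5.1.5.6 has QTcF recorded. Section 9.3 bars anyone who meets an exclusion criterion from receiving study drug. A QTcF is therefore available on the day of dosing, and the 28-day figure does not apply to it. A sentence linking that ECG to exclusion 10 would be clarification only.

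**Conclusion.** The point holds for the pregnancy test. Table 6 does not deliver by test the re-confirmation that 9.1.1.1 promises for the pregnancy part of exclusion 18, and the result relied on may be up to 28 days old rather than 3. Step 5 of 9.4.3 should be reconciled with 9.1.1.1 as a matter of wording. The conclusion rests on Table 6 as printed and on Screening falling more than 3 days before the first dose.

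The documents do not give the expected number of women of childbearing potential or any rate of conception in the window, so no probability can be attached. The event is probably rare in a cohort of six.

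A reader might go further and infer a loss of one subject in six from the DLT Analysis Set. That would be division without an event probability. Subjects who are not evaluable for DLT are replaced under 9.1.2, and neither document defines the major protocol deviations that would exclude a subject dosed in accordance with the schedule. The case for change is subject safety and internal consistency, not precision of the primary endpoint.

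**What to change.** 1. **Table 6:** reconcile it with 9.1.1.1 by marking the pregnancy test, for women of childbearing potential, in the Baseline column in addition to Screening. Footnote a would still let a screening test within 3 days of the first dose serve. The Screening test should stay. Enrollment under 9.1.1.1, and the sponsor's confirmation and registration in 9.4.3 steps 3 and 4, rest on screening and need a pregnancy result at that stage.

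2. **Section 9.4.3 step 5:** base the final confirmation on the results of the screening and baseline assessments, so that it agrees with 9.1.1.1.

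The cost is one table entry and one phrase. No visit is added, and blood and urine are already collected at Baseline. The burden is at most one extra hCG test for each woman of childbearing potential. A rare patient may be found ineligible only in the last 3 days, after registration, and would need to be replaced before dosing.
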